#### **Resources necessary for human research protection**

Describe research staff and justify that the staff are adequate in number and qualifications to conduct the research. Describe how you will ensure that all staff assisting with the research are adequately informed about the protocol and their research related duties. Please allow adequate time for the researchers to conduct and complete the research. Please confirm that there are adequate facilities for the research.

All investigators and research staff on this protocol are well trained on the study and all have current CITI certifications. They are attending physicians that will be caring for this patient population as standard of care and will be involved in every aspect of study procedures.

## **Characteristics of the Study Population**

### **Target population**

Cirrhotic patients admitted to the Hepatology service at the Hospital of the University of Pennsylvania and who are between the ages of 18 and 80 will be eligible for study enrollment. Patients with a history of liver transplantation and recurrent cirrhosis for which they are admitted to the Hepatology service are also eligible for enrollment. Patients being discharged to hospice or those who have a disease process other than cirrhosis (such as severe heart disease or cancer) accounting for a high chance of mortality in the next six months will be excluded.

**Subjects enrolled by Penn Researchers**

426

**Subjects enrolled by Collaborating Researchers**

0

**Accrual**

Penn is a leading liver transplant center, and therefore treats hundreds of patients with liver cirrhosis. The investigators on this protocol are the Hepatology attending physicians and therefore will be treating these patients as standard of care. The study population will be drawn from adults who have been admitted to the Hepatology service at the Hospital of the University of Pennsylvania and the Gastroenterology clinic. [name] and the research staff will identify subjects.

**Key inclusion criteria**

1. Cirrhotic patients between the ages of 18-80 years old 2. Admitted to the Hospital of the University of Pennsylvania or an outside hospital in the last 30 days 3. Ability to consent for themselves or surrogate can consent. 4. Ability to read and provide informed consent in English. 4. Possess a cell phone and willing to receive text messages.

**Key exclusion criteria**

1. Inability to provide informed consent or do not have a surrogate who can provide consent 2. Patients discharged to hospice or those who have a disease process other than cirrhosis (such as severe heart disease or cancer) accounting for a high chance of mortality in the next six months will be excluded. 3. Individuals actively using illicit substances of alcohol. 4. Does not have access to a cell phone with text capability.

**Vulnerable Populations**

Children Form
 
Pregnant women (if the study procedures may affect the condition of the pregnant woman or fetus) Form
 
Fetuses and/or Neonates Form
 
Prisoners Form
 
Other
 
 None of the above populations are included in the research study

--

**The following documents are currently attached to this item:**

*There are no documents attached for this item.*

**Populations vulnerable to undue influence or coercion**

Although not directly targeted, mentally disabled persons, economically or educationally disadvantaged persons, and/or employees or students of the University of Pennsylvania will not be denied enrollment and any special protections and/or additional safeguards will be undertaken in order to protect the rights and welfare of these subjects from coercion or undue influence as appropriate.

**Subject recruitment**

Study recruitment will be accomplished by personal interviews conducted by the PI or study staff prior to discharge from an inpatient hospitalization at the University of Pennsylvania or during a scheduled clinic visit. Patients will be screened and approved by the study investigator prior to contact. We will call potential patients to gauge interest in the study and set up a time to consent in person or over the phone. Potential study subjects will be informed of the criteria for study inclusion, data to be collected during study inclusion, as well as the risks and benefits of study enrollment. This information will be provided in the body of the consent form as well as presented verbally during the consent process. Consent will be documented by signature of the subject and will be witnessed by clinical personnel not affiliated with the study. A copy of the signed consent will then be provided to the subject for their records.

Will the recruitment plan propose to use any Penn media services (communications, marketing, etc.) for outreach via social media avenues (examples include: Facebook, Twitter, blogging, texting, etc.) or does the study team plan to directly use social media to recruit for the research?

No

**The following documents are currently attached to this item:**

*There are no documents attached for this item.*

**Subject compensation\***

Will subjects be financially compensated for their participation?

Yes

**The following documents are currently attached to this item:**

*There are no documents attached for this item.*

**If there is subject compensation, provide the schedule for compensation per study visit or session and total amount for entire participation, either as text or separate document**

All participants, regardless of which arm to which they are randomized, will receive \$25 after 30 days of enrollment and \$25 after 90 days of enrollment (end of observation period) as long as they remain enrolled in the study. Therefore, all participants will receive a total of \$50 for compensation. Compensation will be provided to participants via the Way to Health Platform via a check generated and sent to their home, assuming participants are willing to provide their social security number and any other additional information required.

## Study Procedures

### Suicidal Ideation and Behavior

Does this research qualify as a clinical investigation that will utilize a test article (ie- drug or biological) which may carry a potential for central nervous system (CNS) effect(s)?

No

### Procedures

All cirrhotics admitted to the Hospital of the University of Pennsylvania between the ages of 18 and 80 will be approached for consent (see attached consent forms in the designated section of the protocol). If patients are missed due to being discharged on the weekend, during a holiday or timing issue, patients may be contacted by phone to enroll in the study. If interested, patients can give verbal consent over the phone or written consent at their following clinic visit. After consent is obtained and information is entered into the Way to Health Platform, the participant will be randomized. During this period of time, the participant will be asked to complete the quality of life assessments/ program surveys. Depending on the group to which they are randomized, those in the intervention group will receive welcome items (scale, stop watch, and binder, all necessary for proper data collection in the intervention group). Those randomized to the usual care arm will receive their standard discharge paperwork. Clinical data (readmissions, reasons for readmissions, and length of stay) will be determined for both groups at 30 and 90 days. The groups will additionally be asked to complete quality of life assessments at the end of the study period and a program assessment in the middle and end of the protocol. Additionally, as assessment of readmission rates will be determined in both groups for another 90 days after the end of the intervention (to determine if the health behaviors learned in the intervention group are durable and to determine if providing the intervention to those in the usual care arm is beneficial even if there is a delay in initiation).

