#### **Administration of Surveys and/or Process**

Describe the approximate time and frequency for administering surveys and/or evaluations. For surveys, questionnaires and evaluations presented to groups and in settings such as high schools, focus group sessions or community treatment centers explain how the process will be administered and who will oversee the process. For instance, discuss the potential issues of having teachers and other school personnel administer instruments to minors who are students especially if the content is sensitive in nature. Describe the procedure for audio and videotaping individual interviews and/or focus groups and the storage of the tapes. For instance, if audio tape recording is to be used in a classroom setting, describe how this will be managed if individuals in the class are not participating in the study. Explain if the research involves the review of records (including public databases or registries) with identifiable private information. If so, describe the type of information gathered from the records and if identifiers will be collected and retained with the data after it is retrieved. Describe the kinds of identifiers to be obtained, (i.e. names, social security numbers) and how long the identifiers will be retained and justification for use.

All participants randomized will take a pre and post study quality of life assessment (SF-36 and CLDQ, as described previously) and evaluate the program three times during the study period (90 days). Participants randomized to the telehealth intervention arm will also complete surveys / symptom questionnaires on a daily basis through the SMS feature provided through Way to Health, as outlined above. Data will be transmitted directly to the Way to Health platform and stored securely. Identifiers such as name, address, date of birth and social security number will be entered into the platform at enrollment. Only de-identified data will be available for review/ analysis. Additionally, access to the Way to Health Platform is password protected and access to data will be assigned and be commensurate with nature study staff involvement.

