#### **Secondary outcome variable(s)**

An improvement in patient, provider and caregiver satisfaction post-discharge.

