#### **Design**

A randomized controlled trial will be conducted. The 2 potential groups to which patients may be randomized are: 1) a simple telehealth intervention that utilizes the Way to Health Platform to send SMS messages directly, and 2) standard of care. Given that assignment to the interventions will be obvious to the participants, study staff and investigators, no blinding procedures will be employed. Of note, any participant randomized to the usual care arm will be offered 90 days of telehealth monitoring after study completion.

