**Analysis Plan**

The primary analysis will include a comparison of the demographics and clinical data for the intervention group and the usual care group. To determine if there is a difference in the rates of readmission between the groups, univariable logistic regression analysis will be performed. Any predictors which were different between the groups will be used for adjustment in a multivariable logistic regression. We plan to analyze the data at the 6 month mark. If a significant difference is found, given the low cost of the intervention and potential benefits, the study will be stopped and all patients admitted to the hepatology service will be eligible for telehealth monitoring. Data for the secondary outcomes including changes in quality of life and patient satisfaction will be explored.

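### The protocol does not fix the baseline quality-of-life surveys before randomisation, so in an open-label trial the baseline may be answered with the arm already known

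*Protocol*

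**What the plan says.** The Procedures section sets out enrolment in sequence. First: "After consent is obtained and information is entered into the Way to Health Platform, the participant will be randomized". The next sentence is: "During this period of time, the participant will be asked to complete the quality of life assessments/ program surveys". The arm-specific step follows: "Depending on the group to which they are randomized, those in the intervention group will receive welcome items".

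The section on administration of surveys describes who takes the baseline: "All participants randomized will take a pre and post study quality of life assessment", naming the SF-36 and CLDQ.

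On blinding, the Design section says: "Given that assignment to the interventions will be obvious to the participants, study staff and investigators, no blinding procedures will be employed".

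On the use of these data, the Analysis Plan says: "Data for the secondary outcomes including changes in quality of life and patient satisfaction will be explored". The second overall objective also mentions impact on quality of life. The field for secondary outcome variables lists only satisfaction: "An improvement in patient, provider and caregiver satisfaction post-discharge".

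**The concern.** A baseline is useful for a between-arm comparison because the treatment assignment cannot have influenced it. For a self-reported instrument in an open-label trial, that holds only if the questionnaire is answered before the participant learns the arm. Here randomisation is described before the surveys, and the pre-study assessment is assigned to people already randomised.

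If participants answer with the arm known, pleasure at receiving telehealth or disappointment at usual care can enter the baseline score. A change from that baseline then carries the reaction to allocation with its sign reversed. Enrolment may take place on the ward, in clinic or by telephone, so the order could also differ from patient to patient.

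This belongs in the protocol because it governs how data are collected. No later analysis plan can recover a pre-allocation baseline that was never taken.

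**Working it through.** **What the text fixes.** The protocol states no figure that depends on this order, so there is nothing to reproduce. Set side by side:

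- Procedures: the surveys are first mentioned after randomisation, within a period that is not defined.
- Administration of surveys: the pre-study assessment is given to randomised participants. This identifies who is surveyed; the only timing word is that the assessment is a pre-study one.
- Design: the arm is obvious to participants and staff.
- No section requires the baseline to precede randomisation or disclosure of the arm, and none states that it must follow.

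The order is therefore open, and a baseline taken with the arm known complies with the protocol.

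**Illustration of size.** Inputs from the protocol: 426 participants at 1:1, so n = 213 per arm. Assumed, because the documents give no values: unit SD at both time points, an upward shift d of 0.05 to 0.20 SD in the intervention arm's baseline, a baseline-to-end correlation r of 0.3 to 0.7, no true effect, a two-sided 5% test and a normal approximation. The protocol names no model for quality of life, so three are compared.

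- Change score: bias = −d; SE = √[2(1−r)·2/n]
- ANCOVA on baseline: bias = −r·d; SE = √[(1−r²)·2/n]
- End score alone: bias = 0
- Error rate = P(|Z + bias/SE| > 1.96)

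For r = 0.5 and d = 0.10:

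- Change score: SE = √(2/213) = 0.0969; |bias|/SE = 1.032; error = P(Z > 0.928) + P(Z > 2.992) = 0.177 + 0.001 = 0.178.
- ANCOVA: SE = √(0.75·2/213) = 0.0839; bias = −0.05; |bias|/SE = 0.596; error = P(Z > 1.364) + P(Z > 2.556) = 0.086 + 0.005 ≈ 0.092.

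Two-sided error rates over the assumed range:

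| r | d (SD) | Change score | ANCOVA |
|---|---|---|---|
| 0.3 | 0.05 | 0.072 | 0.053 |
| 0.3 | 0.10 | 0.141 | 0.062 |
| 0.3 | 0.20 | 0.415 | 0.099 |
| 0.5 | 0.05 | 0.081 | 0.060 |
| 0.5 | 0.10 | 0.178 | 0.092 |
| 0.5 | 0.20 | 0.541 | 0.222 |
| 0.7 | 0.05 | 0.102 | 0.080 |
| 0.7 | 0.10 | 0.266 | 0.173 |
| 0.7 | 0.20 | 0.759 | 0.525 |

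**Direction.** Enthusiasm raises the intervention baseline and disappointment lowers the control baseline. Both make the telehealth arm's change look smaller. In the worked change-score case, 0.177 of the 0.178 is rejection in favour of usual care. Rejection in favour of telehealth falls to about 0.001, against a nominal 0.025.

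**After the fix.** If the surveys are answered before the arm is known, d = 0. The bias from this source is then zero and the error rate stays at 0.05 under any of the three models.

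**The case against.** A reader might infer that the protocol places the baseline surveys after randomisation. The documents do not support that. The undefined period can cover the whole window of consent, data entry and randomisation. Information is entered on the platform before randomisation, and the platform also collects survey data, so the baseline could belong to that step. The welcome items are mentioned after the surveys, so they do not show that the arm was known when the surveys were answered. The flow diagrams to which the protocol refers are not available here. This objection stands: the finding is that the order is not fixed, not that it is wrong.

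A reader might also take the error rates as the trial's real risk of falsely claiming a telehealth benefit. They are not. The shift and the correlation are assumed, no evidence of a shift is offered, the model is unspecified, and the likely direction is against telehealth.

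Nor does it add much that patients who leave on learning their arm would lack a baseline: they would also lack an end-of-study score, so their change is missing whatever the order.

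Finally, quality of life is to be explored only and is absent from the secondary outcome field. This limits the weight of the point. It does not remove it, because the Analysis Plan names change in quality of life among the secondary outcomes.

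**Conclusion.** The point holds in limited form. The protocol permits a baseline SF-36 and CLDQ answered with the arm known, and a between-arm change from such a baseline can be biased, most plausibly by hiding a benefit of telehealth. The size cannot be derived from the documents. At an assumed 0.10 SD shift, the error rate is 14% to 27% for change scores and 6% to 17% for ANCOVA as the correlation runs from 0.3 to 0.7; end scores alone are unaffected. Only the exploratory quality-of-life change is at risk; the primary readmission comparison is untouched. Open-label reporting at the end of the study is a separate matter that reordering would not cure. The change is worth making because it is cheap and cannot be made afterwards.

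**What to change.** In the Procedures section, give the order explicitly: consent; baseline SF-36, CLDQ and any baseline program survey; then randomisation and disclosure of the arm. In the section on administration of surveys, assign the pre-study assessment to *all consented participants, before randomisation*. Have the platform, which already collects surveys and randomises, record the time of each step.

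Do not make survey completion a condition of randomisation. The protocol allows surrogate consent for patients with encephalopathy, and telephone consent after discharge, when the 90-day follow-up has already begun. A hard gate could delay such patients or exclude them from the primary comparison in order to protect an exploratory outcome. If a patient cannot complete the surveys, record the baseline as missing and randomise anyway.

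The cost is a slightly longer enrolment step and some missing baselines.

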#### **Primary outcome variable(s)**

A decrease in readmission rates of cirrhotic patients.

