### **Background**

It is well known that patients with cirrhosis have high morbidity and mortality and that early re-hospitalization in any disease process is known to be costly and partially preventable. Few studies exist in the literature on the topic of readmissions in cirrhosis and none use a patient centered approach or a telehealth strategy to reduce readmissions and improve quality of care nor impact quality of life. Volk et al. demonstrated in 2012 that rates of hospital readmission among patients with cirrhosis are higher than other diseases such as CHF, making this patient group at high risk for poor health outcomes. Predictors of readmission include Model For End Stage Liver Disease, MELD, score, serum sodium, and number of concomitant medications used. Frequent readmissions are independently associated with increased mortality, making this not just an economic but also a human concern. The 1st and 2nd most common causes for readmission in cirrhotics are fluid imbalances (overload or dehydration) and hepatic encephalopathy (HE) or confusion resulting from liver disease. Overt HE occurs in 30-40% and minimal HE in 20-80% of patients with cirrhosis. It presents a unique clinical challenge not present in most populations with severe underlying medical conditions as confusion can lead to poor adherence with treatment, making cirrhotics arguably one of the highest risk populations for poor health outcomes. Unfortunately, little attention has been paid to this area thus far. More recently the NACSELD consortium, a 14 center group of liver transplant centers including Penn, showed a 53% 90-day readmission rate for cirrhotics (Bajaj et al). Discrete data from the consortium is limited compared to that from single center studies and no intervention was performed to decrease readmissions or improve patient involvement in their care through this consortium. Authors Tapper, Kumral and Fortune have shown in the last year that readmission rates of cirrhotics at their liver transplant centers are 38%, 62%, and 40%. At The Hospital of the University of Pennsylvania, the 30-day readmission rate for cirrhotic patients is 28%. The hepatology service at the Hospital of The University of Pennsylvania has the highest percentage of potentially preventable readmissions (PPRs) of any service (23.3%) and

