#### **Study duration**

The estimated length of the study will be approximately one year. Each participant will be enrolled for a period of 90 days. The period of follow up will begin on the discharge day and end exactly 90 days from that date. Once patients have completed the 90 days of observation, they are not permitted to be re-enrolled in the study. If a control patient chooses to receive telehealth text messages after the 90 days, they will be in the study for up to 180 days.

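### Death is missing from the 30- and 90-day clinical data, although readmission is compared as a yes/no outcome in a population with high mortality

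*Protocol*

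**What the plan says.** - **Outcome.** Protocol, Primary outcome variable(s): "A decrease in readmission rates of cirrhotic patients". Objectives names two windows, 30 and 90 days.
- **Data.** Protocol, Procedures: "Clinical data (readmissions, reasons for readmissions, and length of stay) will be determined for both groups at 30 and 90 days". Quality-of-life and programme surveys are collected as well. No section lists death as an outcome.
- **Follow-up.** Protocol, Study duration: "The period of follow up will begin on the discharge day and end exactly 90 days from that date".
- **Analysis.** Protocol, Analysis Plan: "To determine if there is a difference in the rates of readmission between the groups, univariable logistic regression analysis will be performed". A multivariable model follows. The data are analysed at 6 months, and a significant difference stops the trial and opens telehealth to all hepatology admissions.
- **Mortality.** Protocol, Background: "It is well known that patients with cirrhosis have high morbidity and mortality", and "Frequent readmissions are independently associated with increased mortality". The exclusion criteria remove hospice discharges and patients with high six-month mortality from disease other than cirrhosis. Patients at risk of liver-related death stay eligible.
- **Monitoring.** Protocol, Data and Safety Monitoring: the investigators monitor the data, adverse events go to the IRB, and there is no DSMB. Nothing links adverse events to the outcome comparison.

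**The concern.** A patient who dies at home on day 20 can no longer be readmitted. If the outcome is simply readmitted or not, that patient falls in the same category as one who stayed well for 90 days. Excluding such patients instead would condition the comparison on survival, which the intervention may affect. Randomisation does not help in either case, because the deaths occur after it.

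The issue matters here for three reasons:

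- The protocol itself describes mortality as high.
- Telehealth is meant to find deterioration early, so it could plausibly turn a death at home into an admission. That would count against it on readmission alone.
- A significant readmission difference at 6 months ends the trial, and the protocol plans no mortality comparison to set beside it.

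**Working it through.** **The plan's own figure.** Approximately 426 patients allocated 1:1 gives 213 per arm. Alpha, power and effect size are not stated, so 426 cannot be reproduced uniquely. Back-solving at two-sided 0.05 and 80% power without dropout, it fits about 53% vs 39.5%, or about 28% vs 16.7%. The control rates are in Background: 53% is the consortium's 90-day rate and 28% the site's own 30-day rate. The telehealth rates of 39.5% and 16.7% are derived, so the 80% starting point holds by construction.

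**Formula.** For control rate p1 and telehealth rate p2, with n = 213 per arm, d = p1 − p2 and p̄ = (p1 + p2)/2:

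- s0 = √[2p̄(1 − p̄)/n]
- s1 = √{[p1(1 − p1) + p2(1 − p2)]/n}
- chance of a significant result favouring telehealth = Φ[(d − 1.96·s0)/s1]

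Check at 53% vs 39.5%: d = 0.135, s0 = 0.0483, s1 = 0.0479. Then (0.135 − 0.0947)/0.0479 = 0.84, and Φ = 80%.

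**A. Masked benefit.** Telehealth moves x percentage points of patients from unreadmitted death to readmission. This is the worst case, in which every averted death is readmitted. Telehealth's readmission rate rises by x.

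| x (assumed) | 90 days | Power | 30 days | Power |
|---|---|---|---|---|
| 0 | 53% vs 39.5% | 80% | 28% vs 16.7% | 80% |
| 2 | 53% vs 41.5% | 66% | 28% vs 18.7% | 62% |
| 3 | 53% vs 42.5% | 58% | 28% vs 19.7% | 52% |
| 5 | 53% vs 44.5% | 42% | 28% vs 21.7% | 32% |

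The composite does not lose this difference. If unreadmitted death is D in controls and D − x under telehealth, the 90-day composite rates are 53 + D and 39.5 + x + D − x = 39.5 + D, which still differ by 13.5 points. With D = 5% (58% vs 44.5%) or D = 10% (63% vs 49.5%), composite power is 80%. At 30 days with D = 5% (33% vs 21.7%) it is 74%, so the composite has a small cost of its own there.

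**B. Apparent benefit.** Readmission-or-death is equal in both arms, but y points more telehealth patients die before readmission. Their readmission rate is then y points lower.

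| y (assumed) | Readmission | Chance of a significant result favouring telehealth |
|---|---|---|
| 0 | 53% vs 53% | 2.5% |
| 3 | 53% vs 50% | 9.0% |
| 5 | 53% vs 48% | 17.6% |

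For y = 5: d = 0.05, s0 = 0.04845, s1 = 0.04839. Then (0.05 − 0.09496)/0.04839 = −0.93, and Φ = 17.6%.

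**The case against.** **A SAP may deal with this.** How deaths are coded, a supportive composite and a table of deaths by arm commonly belong in the SAP, which is not shown; their absence here would not be a finding. That stands. The data list, however, is in the protocol and omits death. No later analysis rule can recover vital status that was never ascertained, least of all for deaths outside the hospital. The list may be only a summary and adverse-event reports may reveal some deaths, but nothing in the protocol makes that complete or equal between arms.

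**Readings that go too far.**
- A reader might infer that the protocol scores an unreadmitted death as a success. It gives no rule. That coding is the default of a yes/no variable, not a stated choice.
- A reader might infer that only readmissions are collected. Reasons for readmission, length of stay, quality of life and satisfaction are collected too.
- A reader might take 53% vs 39.5% as the design assumption. It is back-solved.
- A reader might call scenario B an inflated type I error. On readmission itself, 53% vs 50% is a true difference. It misleads only when read as patient benefit. The reference for results favouring telehealth is 2.5%, one side of a two-sided 5% test.

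**Plausibility.** The documents give no mortality figure to support shifts of 2 to 5 points, and scenario A takes the worst case. The mechanism in the protocol, early detection, points to A. Nothing in it suggests that telehealth would raise early deaths, so B shows what could go undetected and is not a prediction. All of this stands.

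**Conclusion.** The point holds in a limited form. The protocol fixes a readmission outcome, a logistic comparison that can stop the trial, and a 30/90-day clinical data list without death, in patients it describes as having high mortality. An imbalance in early deaths could distort the comparison in either direction, and the listed data would not reveal it.

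The direction of each distortion follows from the outcome definition. Its size rests on assumptions: 213 per arm, two-sided 0.05, a single analysis, the back-solved rates and the assumed death shifts. On those, a shift of 2 to 5 points cuts power from 80% to between 66% and 42% at 90 days, and to between 62% and 32% at 30 days. In the opposite scenario, 3 or 5 points give about a 9% or 18% chance of a significant result favouring telehealth with no gain on readmission-or-death. The documents do not support saying that either distortion will occur. This should be changed, but it does not invalidate readmission as the primary outcome.

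**What to change.** 1. Under Procedures, add vital status and date of death to the 30- and 90-day data. Ascertain them the same way in both arms, from the chart plus the contacts already made around those times, because deaths elsewhere may not appear in site records.
2. Keep readmission as the primary outcome and state how patients who die unreadmitted are counted.
3. Pre-specify readmission-or-death, at the same windows and with the same logistic model, as the key supportive analysis.
4. Report unreadmitted deaths by arm.
5. Show items 3 and 4 beside the readmission result at the 6-month look and in any claim of benefit. Define consistency as a composite odds ratio also below 1. This is only a check of direction: with truly equal composites, chance alone puts the odds ratio below 1 about half the time. The deaths by arm must therefore be shown with it.

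The cost is two data fields, some extra follow-up work for deaths outside the hospital, and one more model. The downside is that a gain in readmission alone, not supported by the composite, would be reported more cautiously.
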